Efficacy and Safety of Oral RPC1063 in RMS Patients

#### Footnotes to Table 3

- 1 At Visit 1 an interim medical history will be performed to complete the screening medical history. Medical events that occur between screening and first dose will be recorded as medical history. All SAEs must be reported from the time of signing the informed consent; AEs are collected after the first dose.
- 2 Laboratory tests include Hematology, Chemistry, and Urinalysis.
- 3 Serum beta-hCG at screening, urine beta-hCG at each visit. If the urine pregnancy test is positive, do not dose and confirm with a serum pregnancy test.
- 4 Serology testing will be performed at screening to determine the patient's immune status with respect to the following viruses: Human immunodeficiency virus (HIV) antibodies, anti-hepatitis A virus IgM, hepatitis B surface antigen (HBsAg) and anti-hepatitis B core antigen (HBcAg) IgM, anti-hepatitis C virus (HCV) IgG or IgM. In addition, patients must have documentation of positive Varicella Zoster Virus (VZV) IgG antibody status or complete VZV vaccination at least 30 days prior to first dose of study medication.
- 5 The TB screening test (purified protein derivative) should be performed during the screening period and all testing must be completed prior to administration of study drug on Day 1 As available locally, an interferon gamma release assay such as QuantiFERON Gold test may be used as an alternative screening TB test or as a confirmatory test to rule out a false positive result using purified protein derivative.
- 6 Height at screening only.
- 7 A chest X-ray is not required if performed within 60 days prior to randomization and if documentation is on file.
- 8 Refer to Table 5 for details of cardiac monitoring.
- 9 RPC1063 (0.5 or 1 mg) will be administered daily for the study duration; IFN β-1a 30 μg will be administered by IM injection weekly.
- 10 Brain MRI scans will include a T2 and T1 scan (with and without Gadolinium) and will be performed at screening and then yearly.
- 11 Three MSFC practice assessments must be performed before baseline. These may be performed at the screening visit, or at any time between the screening and baseline visit.

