- 1 The Unscheduled Relapse Assessment Visit will be conducted in the case of a suspected relapse (see Section 9.1.2.3). After the Unscheduled Relapse Assessment Visit, patients should return to their usual visit schedule.
- 2 Patients who prematurely discontinue study treatment will be asked to complete an Early Termination visit.
- 3 Laboratory tests include Hematology, Chemistry, and Urinalysis.
- 4 Urine beta-hCG. If the urine pregnancy test is positive, do not dose and confirm with a serum pregnancy test.
- 5 Brain MRI scans will include a T2 and T1 scan (with and without Gadolinium).
- 6 Pulmonary function tests will include FEV1 and FVC measurements, and DLCO. If any abnormalities occur, they will be followed until such time as resolution is confirmed or no further improvement is expected by the investigator (based on a follow-up period of not less than 3 months).
- 7 If abnormal OCT findings, or visual signs or symptoms of macular edema are observed, a general ophthalmologic examination including eye history, visual acuity, and dilated ophthalmoscopy will also be performed.

Table 5 Cardiac Monitoring During Dose Titration – Days 1, 5, and 8

	Cardiac Monitoring								
	Day 1/Part A Day 169 (W24)			Day 5 				Day 8 	
	Predose	Hourly for 6	At Hour 6	Continuous	Predose	Hourly for	At Hour 6	Continuous	Continuous
		hours		Monitoring		6 hours		Monitoring	Monitoring for 24
				for 24 hours				for 24 hours	hours
Procedure							<	/	
Vital signs	X	X			X	X			
12-lead ECG	$X^2$		X		$X^2$		X		
Holter monitoring 				$X^4$				X	X
Assess Discharge			X 			,	$X^{6,7}$		
Criteria 			Λ			7.	A c ,		

ECG = electrocardiogram

- 1 Day 5 and Day 8 procedures will be conducted in the first 75 patients
- 2 Baseline or predose ECG should be provided by the site and be available for comparison to the postdose ECG in order to determine if discharge criteria are met
- 3Begin 15 minutes predose and continue for 24 hours after dose.
- 4 Holter monitoring will be performed on Day 1 for Part A patients only, and will not be performed in Part B or on the Week 24 (Day 169) visit for Part A.

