#### Investigator decision

The Treating Investigator may discontinue study medication if it is determined that it is not safe or in the patient's best interest to receive further treatment. The Medical Monitor should be promptly notified of the decision.

- Noncompliance: after consultation between the investigator, the Medical Monitor, or Study Monitor, and the sponsor when appropriate, a patient may be discontinued from study medication for failure to comply with protocol requirements
- Intercurrent illness: A patient may be discontinued from study medication if, in the judgment of the treating investigator, the patient develops an intercurrent illness or complication that is not consistent with the protocol requirements or that, in any way, justifies discontinuation of study medication.
- Protocol-defined adverse events of special interest (see Section 12.4):
  - Confirmed AST or ALT >5 times the upper limit of the normal range, confirmed upon retest within 14 days of the original lab value (unless determined by the investigator to not be of hepatic origin)
  - o A diagnosis of macular edema, which is new or worsening since baseline
  - o FEV1 or FVC <50% of predicted values
- If the patient becomes pregnant
- Sponsor termination or suspension of the study

All patients who discontinue study medication should complete an Early Termination Visit (see Table 2 [Part A] and Table 4 [Part B]). Unless the patient withdraws consent or is lost to follow-up, they will be asked to undergo a follow-up visit 4 weeks after the last dose for the collection of safety data including lymphocyte recovery and to assess their disease status. Alternative treatment for multiple sclerosis (with the exception of medication given in the context of another clinical trial) can be started, if needed, after the early termination visit.

The reason for discontinuation of study medication will be recorded in the clinical records and the patient's eCRF.

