#### 9.5. Treatment

#### 9.5.1. Treatments Administered

The Investigator must ensure that the investigational product will be used only in accordance with the protocol.

Part A of the study is randomized and double-blinded with regard to treatment with RPC1063 and matching placebo in order to prevent bias in treatment allocation and in the assessment of effect. The Investigator site personnel, as well as the Sponsor and their representatives involved in the monitoring or conducting the study, and the patients will all be blinded to the study drug codes.

Part B of the study is randomized and double-blind, double-dummy with regards to treatment with RPC1063 or IFN  $\beta$ -1a and their corresponding matching placebo in order to prevent bias in treatment allocation and in the assessment of effect. The prolonged treatment period (24 months) will provide additional safety and efficacy data; information that is relevant to RMS, a chronic, highly variable, slowly progressing disease.

In both Part A and Part B of the study, a "dual assessor" approach will be used to evaluate efficacy and safety to prevent potential unblinding as result of observed efficacy, AEs, or laboratory changes

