Three sensitivity analyses will be performed: the first will repeat the primary GdE analysis using the mean number of GdE lesions from patients from the same treatment group to impute missing GdE values. The second will repeat the primary GdE analysis using last observation carried forward (LOCF) method for imputing missing GdE data

values. Only data from post-Baseline MRI scans can be carried forward to the Month 24 timepoint for this analysis. The third will repeat the primary GdE analysis using only patients with complete GdE data at Month 24 (observed cases analysis). All three sensitivity analyses will include the natural log transformation of exposure time on study (instead of the number of available MRI scans) as the offset term.

All GdE lesion results will be listed

Key Secondary Endpoint: Time to onset of disability progression as defined by a sustained worsening in EDSS of 1.0 points or more, confirmed after 3 months and after 6 months

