## 9.3. Other Secondary Efficacy Endpoints

The other secondary endpoints are:

- Proportion of patients who are GdE lesion-free at Month 24
- Proportion of patients who are new or enlarging T2 lesion-free at Month 24
- Percent change in normalized brain volume (atrophy) on MRI scans from Baseline to Month 24
- Change in MSFC score from Baseline to Month 24 (including the low-contrast letter acuity test [LCLA] measurement of visual function as a component)
- Change in MSQOL-54 score from Baseline to Month 24

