### 9.3.1. Analysis

Secondary Endpoints: The proportion of patients who are GdE lesion-free at Month 24, and the proportion of patients who are T2 lesion-free at Month 24

Each of these endpoints will be analyzed using a Cochran-Mantel-Haenszel (CMH) test

stratified by region and EDSS category at Baseline. The numbers and percentages of patients with 0, 1-2, 3-4, and  $\geq$  5 lesions will be reported. The proportion of patients who are lesion-free will be reported along with the associated 95% CI. The difference in proportions between each RPC1063 group and the IFN  $\beta$ -1a group will also be reported with the associated 95% CI and CMH p-value. Patients who are missing the Month 24 MRI data will be considered non-responders, i.e., as not being lesion-free.

Sensitivity analyses will be conducted using the LOCF method for replacing missing Month 24 MRI data and on the subset of patients with non-missing Month 24 MRI data (observed cases analysis).

Secondary Endpoint: Change in normalized brain volume (atrophy) on MRI scans from Baseline to Month 24

Brain volumes will be reported in cm^3. If the data are collected in mm^3, then a transformation will be applied by dividing the result in mm^3 by 1000 to convert to cm^3 prior to analysis.

Actual brain volumes, change from Baseline to each visit, and percent change from Baseline to each visit will be summarized. Comparisons of the change and percent changes between the treatment groups will be analyzed using an analysis of covariance (ANCOVA) model adjusted for region, EDSS category at Baseline, and brain volume at Baseline. The mean difference between each RPC1063 treatment group and IFN  $\beta$ -1a will be reported with the associated 95% CI and p-value. Patients with missing data will have their results imputed via LOCF.

Secondary Endpoint: Change in MSFC score from Baseline to Month 24 (including the low-contrast letter acuity test [LCLA] measurement of visual function as a component)

The MSFC score is a battery of the following 3 individual scales:

- The Timed 25-Foot Walk is a quantitative measure of lower extremity function
- The 9-Hole Peg Test is a quantitative measure of upper extremity (arm and hand) function
- The Symbol Digit Modalities Test (SDMT) is a measure of cognitive impairment that assesses attention, visuoperceptual processing, working memory, and psychomotor speed

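### LOCF as the only brain-volume analysis understates expected 24-month loss, by roughly 6% to 13% of the arm mean at planned dropout, and unequal dropout can bias the contrast either way

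*SAP*

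**What the plan says.** SAP 9.3 lists the endpoint among the other secondary endpoints: "Percent change in normalized brain volume (atrophy) on MRI scans from Baseline to Month 24". SAP 9.3.1 compares change and percent change by an ANCOVA "model adjusted for region, EDSS category at Baseline, and brain volume at Baseline", each RPC1063 dose against IFN β-1a, and closes the paragraph with "Patients with missing data will have their results imputed via LOCF". It gives no alternative analysis, although Protocol 13.6.1 leaves the Part B missing-data sensitivity analyses to the SAP.

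The SAP does more for its other endpoints:

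- Lesion counts (9.2.1) have mean-imputation, LOCF and observed-case sensitivity analyses, and LOCF is restricted. For GdE lesions, "Only data from post-Baseline MRI scans can be carried forward to the Month 24 timepoint"; the T2 paragraph has the same limit.
- Lesion-free proportions (9.3.1) have LOCF and observed-case sensitivity analyses.
- MSQOL-54 (9.3.1) has missing values imputed from a random slope and intercept model.

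On the data available, Protocol Table 3, footnote 10, says brain MRI "will be performed at screening and then yearly", that is, at screening, Month 12 and Month 24. Protocol Table 4, footnote 2, adds: "Patients who prematurely discontinue study treatment will be asked to complete an Early Termination visit". That visit includes a brain MRI (Table 4; Protocol 10.5). After it, Protocol 9.4.4.1 says of these patients that "they will be asked to undergo a follow-up visit 4 weeks after the last dose", and that visit has no MRI (Protocol 10.6).

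**The concern.** Protocol 9.5.1 describes RMS as "a chronic, highly variable, slowly progressing disease". For a quantity that declines on average, carrying the last scan forward credits the patient with no further loss. With yearly scans the carried value may be a year old. The brain-volume sentence does not say that baseline may not be carried, which would record no change at all.

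At stake is the Month 24 atrophy contrast for both doses. Its bias depends on how many patients lack a Month 24 scan in each arm and when they left, not only on the drug. With no second analysis planned, the report would not show how much of the estimate the rule produced.

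Missing scans need not come only from dropout. Protocol 11.1.1 postpones MRI until 30 days after methylprednisolone for a relapse, and SAP 5.4.3 accepts Month 24 MRI only on Days 706 to 734. A late relapse can therefore push a completer's scan outside the window.

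**Working it through.** **Inputs from the documents.** Dropout is about 12% in SAP 5.1 and 17% in Protocol 13.2. Both lead to about 400 per arm: 353/0.88 = 401.1 and 333/0.83 = 401.2, each rounding up to 402. The documents give no atrophy rate, SD or sample size for brain volume, so there is no planned figure for this endpoint to reproduce.

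**Assumptions.** Loss is linear at r per year (true 24-month loss 2r). Dropout proportion is d, with timing uniform over 24 months.

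**Step 1: arm mean.**

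- *Early Termination scan carried.* Mean time remaining is 1 year, so the mean shortfall per dropout is r. Relative understatement = d × r / 2r = d/2, which is 6.0% at 12% and 8.5% at 17%.
- *Scheduled scans only, baseline allowed.* Half the dropouts leave before Month 12 and fall short by 2r; half leave later and fall short by r. The mean is 1.5r, and the understatement 0.75d: 9.0% at 12% and 12.75% at 17%.
- *Month 12 carried, earlier dropouts excluded.* (d/4)/(1 − d/2), which is 0.03/0.94 = 3.2% and 0.0425/0.915 = 4.6%.

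These percentages do not depend on r. At an assumed r of 0.4% per year the true loss is 0.80%. LOCF gives 0.752% and 0.732% with the Early Termination scan, or 0.728% and 0.698% with scheduled scans only.

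**Step 2: the contrast when the drug works.** Set IFN loss to 1 and assume RPC1063 loses 25% less, so the true difference is 0.25. Observed arm mean = L × (1 − s × d), with s = 0.5 (Early Termination scan carried) or 0.75 (scheduled scans only). Dropout splits other than 12/12 and 17/17 are illustrations.

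| Dropout IFN / RPC1063 | s = 0.5 | s = 0.75 |
|---|---|---|
| 12% / 12% | 0.235 (−6%) | 0.2275 (−9%) |
| 17% / 17% | 0.229 (−8.5%) | 0.218 (−12.75%) |
| 12% / 15% | 0.246 (−1.5%) | 0.244 (−2.25%) |
| 12% / 16% | 0.250 (0%) | 0.250 (0%) |
| 12% / 20% | 0.265 (+6%) | 0.2725 (+9%) |
| 20% / 12% | 0.195 (−22%) | 0.1675 (−33%) |

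The bias is s × (0.75 × d_RPC − d_IFN). It favours RPC1063 only when d_RPC/d_IFN exceeds 1/0.75 = 1.33.

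**Step 3: the contrast when true loss is equal.** With dropout of 10% and 20%, the higher-dropout arm gains 0.10 × r = 0.04 percentage points at r = 0.4 (0.02 to 0.06 for r = 0.2 to 0.6). With scheduled scans only, the gain is 0.15 × r = 0.06 (0.03 to 0.09). At 400 per arm and an assumed SD of 0.8, the standard error is 0.8 × √(2/400) = 0.0566. A bias of 0.04 then raises a nominal two-sided 5% error to 10.9%, and 0.06 raises it to 18.6%. At an SD of 1.5 these are 6.6% and 8.7%.

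**The case against.** The strongest defence is that the bias is small and usually conservative. The Early Termination MRI supplies a late value for many who leave. SAP 5.4.3 defines the last available assessment, for all efficacy parameters, as the latest on-treatment value from any visit. The baseline MRI is done at screening, before treatment, so it arguably cannot be carried. With similar dropout in the arms, LOCF shrinks a true difference, which does not help a superiority claim. The endpoint is outside the multiplicity procedure (SAP 5), and the primary and key secondary analyses are untouched.

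Most of this stands and limits the size. It does not defend LOCF as the only analysis. The Early Termination scan reduces the mean shortfall per dropout from 1.5r to r and does not remove it. The on-treatment wording is also double-edged: a scan taken after treatment stops may not qualify, and one outside the SAP 5.4.3 windows belongs to no defined visit. Which scans may be carried therefore remains unclear.

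Three stronger readings are tempting but unsupported:

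- *Every dropout's loss is understated.* This is true in expectation only. With an assumed mean loss of 0.4% per year, and assumed slope variation or scan noise, about 73% to 98% of dropouts are understated.
- *The arm with more dropout always looks better.* This holds when true loss and dropout timing are equal across arms. At 12% against 15% with a 25% effect, RPC1063 has more dropout and its benefit is still understated.
- *Baseline is carried for every dropout*, so 17% dropout would cost 17% of the loss. That needs every dropout to have neither a Month 12 nor an Early Termination scan.

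**Conclusion.** The concern holds in a limited form. LOCF, as the sole handling of missing brain volume, understates expected 24-month loss among patients without a Month 24 scan. Under linear loss and uniform dropout timing, the arm mean is understated by 6% to 8.5% with the Early Termination scan, or 9% to about 13% with scheduled scans including baseline. If early leavers are excluded instead, it is 3.2% to 4.6%. The direction of bias in the contrast depends on dropout and true loss together, so it cannot be called in advance. Atrophy rates, SDs, the 25% effect and the unequal dropout splits are assumptions; only the 12% and 17% come from the documents. This should be corrected, but it concerns one secondary endpoint without alpha control.

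**What to change.** Make the primary brain-volume analysis a likelihood-based longitudinal model of percent change that uses all post-baseline scans at their actual dates, including Early Termination and out-of-window scans. A random intercept and slope model adjusted for region, EDSS category and baseline volume would do. Report the Month 24 contrast for each dose. A visit-based repeated-measures model at Months 12 and 24 is weaker here, because it would discard Early Termination scans outside the SAP 5.4.3 windows.

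Keep LOCF and observed cases as sensitivity analyses. Restrict LOCF to post-baseline scans, and state whether an Early Termination scan may be carried.

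The cost is SAP wording and one model of a kind already used for MSQOL-54; no new data are needed. The downside is that the model assumes data missing at random and a form for the time course, which yearly scans can test only weakly.

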The MSFC z-score is calculated by creating z-scores for each component of the MSFC, as explained below, and averaging them to create an overall composite score, i.e.,

MSFC z-score = 
$$(Z_{25\text{-foot-walk}} + Z_{9HPT} + Z_{SDMT})/3$$
, and

MSFC z-score (LCLA) =  $(Z_{25\text{-foot-walk}} + Z_{9\text{HPT}} + Z_{SDMT} + Z_{LCLA})/4$ , where  $Z_{xxx}$  refers to Z-scores

A z-score represents the number of standard deviations a patient's test result is higher (z > 0) or lower (z < 0) than the average test result (z = 0) of the reference population.

The following describes the scoring, and rules for missing value imputation for each component.

Timed 25-Foot Walk Z-score Calculation

The Z-score is calculated as in the following formula:

$$Z_{25\text{-foot-walk}} = (-1) * \frac{((t_1 + t_2)/2) - MEAN(reference)}{SD(reference)}$$

where  $t_1$  and  $t_2$  are the time (in seconds) from the two trials, and the mean (reference) and SD (reference) are the mean and standard deviation respectively, of baseline values for the reference population. The reference population will be the study population.

For missing post-Baseline values, if a patient is missing only one trial for any post-Baseline visit, then the score from the non-missing trial will be used to calculate the Z-score. The steps outlined above will remain the same except the actual times will not be averaged.

The missing data algorithm suggested by the MSFC manual will be used to impute missing values. If both scores from the two trials are missing for any post-Baseline visit, due to MS related physical limitation or other physical limitations, then the patient will be given a Z-score of -13.7 for the Timed 25-Foot walk. If the reasons for missing scores on both trials are due to other reasons (non-compliance, missed visits), then LOCF from post-Baseline values will also be used as to impute the z-score for that visit. If a value is not available to carry forward, the mean of the available z-scores using all available data from the same treatment group, will be calculated at the specified visit and used as the imputed value. Values imputed using the mean will not be carried forward to other visits.

If a patient has missing data at Baseline for either trial, then the mean of the available z-scores will be evaluated by treatment group and used as the imputed value.

9HPT Z-score Calculation

Z-score for the 9HPT is calculated as in the following formula:

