$$Z_{9HPT} = \frac{((\frac{1}{(t_{11} + t_{12})/2} + \frac{1}{(t_{21} + t_{22})/2})/2) - MEAN(reference)}{SD(reference)}$$

where  $t_{11}$ ,  $t_{12}$ ,  $t_{21}$ ,  $t_{22}$  are the time (in seconds) taken to complete for dominant hand trial 1, dominant hand trial 2, non-dominant hand trial 1, and non-dominant hand trial 2, respectively. The mean (reference) and SD (reference) are the mean and standard deviation, respectively, of reference population's baseline score. The reference

population will be the study population.

For missing post-Baseline values, if any of the times from the two trials of the same hand is missing, then the score from the non-missing time will be used to calculate the Z-score. The steps outlined above will remain the same except the actual times will not be averaged.

The missing data algorithm suggested by the MSFC manual will be used to impute missing values. If both scores from either hands are missing for any post-Baseline visit, due to MS related physical limitation or other physical limitations, then the patient will be given a Z-score will be calculated using a value of 777 seconds. If the reasons for missing scores on both trials are due to other reasons (non-compliance, missed visits), then LOCF from post-Baseline values will also be used as to impute the z-score for that visit. If a value is not available to carry forward, the mean of the available z-scores using all available data from the same treatment group, will be calculated at the specified visit and used as the imputed value. Values imputed using the mean will not be carried forward to other visits.

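### Timed 25-Foot Walk scoring discards a measured baseline trial, and sets a fixed -13.7 for inability beside study-standardised z-scores with no floor and no MSFC sensitivity analysis

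*SAP*

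**What the plan says.** The passages are in SAP 9.3.1, in the MSFC part. Protocol 11.1.4 leaves the z-score details to the SAP.

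- **Observed walks.** The z-score is minus (mean of the two times − reference mean) / reference SD, using baseline values. "The reference population will be the study population".
- **Source of the missing-data rule.** "The missing data algorithm suggested by the MSFC manual will be used to impute missing values". The manual is not in the SAP reference list, and the SAP gives no derivation of the constant.
- **Inability after baseline.** If both trials are missing "due to MS related physical limitation or other physical limitations, then the patient will be given a Z-score of -13.7". Other reasons, such as a missed visit, lead to LOCF and, failing that, to the treatment-group mean at that visit.
- **One trial missing after baseline.** The remaining trial is used.
- **Baseline.** "If a patient has missing data at Baseline for either trial, then the mean of the available z-scores will be evaluated by treatment group", and that mean is the imputed value.
- **9-Hole Peg Test, for comparison.** Inability is entered as a time and then standardised: the "Z-score will be calculated using a value of 777 seconds".
- **Use.** The three components (four with LCLA) are averaged. Month 24 change is compared by ANCOVA adjusted for region, EDSS category and baseline MSFC.

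The SAP plans sensitivity analyses for ARR, T2 lesions, GdE lesions, disability progression and the lesion-free proportions. It states none for MSFC.

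**The concern.** Two separate matters arise.

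First, the baseline rule discards data. A patient with one valid baseline walk is treated as if there were none, although the same patient at a later visit would be scored on the single trial. The replacement value depends on assigned arm, while the quantity being filled is a pre-treatment covariate that also enters the change score.

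Second, the walk variable mixes two scales. Completed walks move with the study mean and SD; inability does not. The SAP sets no maximum time and no floor, so nothing guarantees that inability is the worst score. The trigger also covers limitations unrelated to MS, so a leg injury present at Month 24 scores the same as loss of walking from MS. A few values this extreme can carry much of the mean and variance in an ANCOVA.

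At stake is the MSFC comparison, which serves the secondary objective on delaying accumulation of disability (SAP 3, Protocol 8.1.2).

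**Working it through.** **Inputs from the documents:** constant -13.7; linear walk formula; three- and four-part averages (all SAP 9.3.1); 400 patients planned per arm (SAP 5.1); baseline EDSS 0 to 5.0 (Protocol 9.4.1).

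**Assumed, because the documents give no value:** baseline walk mean 5 to 7 s and SD 2 to 4 s; SD of MSFC change 0.4 to 0.5 without any -13.7; 1% of an arm affected.

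The -13.7 cannot be reproduced: no walk mean, SD or maximum time behind it is given.

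**1. Walk time equivalent to -13.7.** Inverting the SAP formula gives t = mean + 13.7 × SD.

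| Mean (s) | SD (s) | Equivalent time (s) |
|---|---|---|
| 5 | 2 | 5 + 27.4 = 32.4 |
| 6 | 3 | 6 + 41.1 = 47.1 |
| 7 | 4 | 7 + 54.8 = 61.8 |

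A slower completed walk scores below inability. With mean 6 s and SD 2 s, a 60 s walk scores -(60 − 6)/2 = -27.0. With SD 5 s it scores -10.8 and the order holds.

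**2. SD below which the order reverses.** This is (T − mean)/13.7. At mean 6 s: 54/13.7 = 3.94 s for a 60 s walk, 114/13.7 = 8.32 s for 120 s, and 174/13.7 = 12.70 s for 180 s.

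**3. Weight in the composite.** -13.7/3 = -4.57 (three parts); -13.7/4 = -3.43 (four parts). Relative to a walk z of 0, one patient in 400 moves the arm mean by -4.57/400 = -0.011, or -3.43/400 = -0.009.

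**4. A 1% imbalance, three-part score.** The shift is 0.01 × 4.57 = 0.046. The variance in the affected arm is (1 − p) × SD² + p(1 − p) × 4.57², with p = 0.01; the second term is 0.206.

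- SD 0.4: 0.158 + 0.206 = 0.365. SE = √[(0.365 + 0.160)/400] = 0.036. Shift/SE = 1.3.
- SD 0.5: 0.248 + 0.206 = 0.454. SE = √[(0.454 + 0.250)/400] = 0.042. Shift/SE = 1.1.

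Without the added variance the SEs would be 0.4 × √(2/400) = 0.028 and 0.5 × √(2/400) = 0.035, which would overstate the ratio.

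**5. Baseline rule.** If the discarded trial lies one reference SD from the arm mean, the baseline walk z is wrong by 1 and the three-part composite by 1/3 = 0.33. The documents do not allow an estimate of how many patients this affects.

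**The case against.** The -13.7 follows a named manual and is specified in advance. It is a choice, not a slip, and changing it would cost comparability with trials that use it. That stands, and it is a reason to keep the value.

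A reader might infer that the scale is in fact reversed at its worst end. The documents do not show this. Reversal needs a completed walk beyond mean + 13.7 × SD, and no walk SD is given. The EDSS cap makes a small SD plausible but also makes very slow walkers and non-walkers uncommon.

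A reader might also infer that inability should be entered as a worst time and standardised, as for the peg test. The parallel fails. The peg-test score uses reciprocals, so 777 s contributes 1/777 = 0.0013, close to the natural floor of zero. The walk score is linear in seconds. An assumed 180 s with mean 6 s and SD 2 s gives -174/2 = -87, which worsens the leverage.

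Nor do the documents support reading the injury rule as a bias between arms. In a randomised, double-blind comparison, injuries unrelated to treatment add noise rather than expected bias, and only those present at Month 24 count in this test. Separating MS from other causes needs an attribution that the SAP does not define, and treating the latter as missing may carry forward an earlier, better score. This argues for a sensitivity analysis rather than a change to the main rule. An imbalance caused by true loss of walking from MS would be treatment effect, not error.

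Finally, the three required MSFC practice sessions before baseline should make a missing baseline trial rare. That limits the size of the baseline problem but does not justify discarding a measurement.

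**Conclusion.** The point holds at modest size. The baseline rule discards a measured trial, uses treatment arm to fill a pre-treatment value, and is inconsistent with the rule after baseline; this rests on the text alone. The inability rule allows a completed walk to score worse than inability and leaves the ANCOVA exposed to a few scores worth -4.57 each on the three-part composite, with no sensitivity analysis to show their influence. Whether any reversal would occur depends on a walk SD that is not in the documents.

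The shift of 0.046, or 1.1 to 1.3 SE, is conditional on a 1% versus 0% split and a change SD of 0.4 to 0.5, all assumed. It illustrates sensitivity and is not a forecast.

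A reader might infer that the trial's disability conclusions as a whole are at risk. They are not. EDSS progression is a separate key secondary endpoint, and MSFC is an other-secondary endpoint tested without multiplicity adjustment (SAP 5). Primary and key secondary results are unchanged.

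**What to change.** In SAP 9.3.1, before database lock:

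1. **Baseline walk.** If one trial is missing, score the available one. If both are missing, use the overall baseline mean across arms, not the arm mean. On the SAP's scale this is essentially 0, because the study's own baseline is the reference.
2. **Inability.** Keep the manual's -13.7, but floor observed walk z-scores at -13.7, so that inability never ranks better than a completed walk.
3. **Sensitivity analyses of Month 24 MSFC change.** Add (a) a rank-based analysis, for example rank ANCOVA with the same covariates, and (b) an analysis treating non-MS physical limitations as missing, handled like missed visits. Analysis (b) should cover the peg test and SDMT too, because their rules name the same causes. It requires the cause of the limitation to be recorded.

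The cost is SAP wording, a little more programming, and a minor departure from the manual's scoring wherever the floor applies. Analysis (b) has the carry-forward weakness noted above, so it should support the main analysis and not replace it.
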